After all subjects have completed the 72-hour assessments in Part 1, an analysis will be conducted in order to select a single therapeutic dose from the three liposome bupivacaine dose levels tested. An unblinded dose selection committee will review at least the results from the following assessments conducted during Part 1: (1) the area under the curve (AUC) of the numeric rating scale (NRS) at rest (NRS-R) pain intensity scores through 72 hours; (2) total postsurgical opioid consumption; (3) the time to first opioid rescue; and (4) safety data. Based on a clinical evaluation of the results the committee will determine the apparent efficacy and safety of each of the three liposome bupivacaine dose levels tested and will recommend a dose level for Part 2 of the study. Statistical significance will not be required in order to recommend a dose level for Part 2. The unblinded dose selection committee also will recommend whether the sample size for Part 2 should be increased.

Part 2

In Part 2 of the study, approximately 180 subjects (randomized 1:1, resulting in approximately 90 liposome bupivacaine subjects and 90 placebo subjects) will receive a single dose injection femoral nerve block with the selected dose of liposome bupivacaine (i.e., 67, 133, or 266 mg) or placebo in 20 mL under ultrasound guidance.

Postsurgical Rescue Medication

Subjects should only receive rescue medication upon request for pain control, as needed.

First Rescue Medication (IV Hydromorphone)

The first rescue medication will be intravenous (IV) hydromorphone 0.5 mg, which will be administered once via bolus only. At this time, the PCA should be loaded with opioid (morphine or hydromorphone only).

Second Rescue Medication (PCA and/or PO Opioid)

The second rescue medication will be an on-demand PCA-administered opioid (morphine or hydromorphone). The PCA pump will be programmed to deliver either on-demand morphine or on-demand hydromorphone boluses at a dose and lockout interval in accordance with the site's standard practice. A continuous infusion (background or basal rate) of morphine or hydromorphone is not permitted. If the subject's pain is excessive or pain control is inadequate, then the bolus dose may be adjusted according to local hospital practices; however, **adding a basal rate is prohibited.**

Once a subject is able to tolerate oral (PO) medication, PO immediate-release oxycodone may be administered (but not more than 10 mg every 4 hours).

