15.5. Handling Subject Dropouts and Discontinuations

For the calculation of AUC of NRS pain intensity scores through any of the time periods, the following methods will be used for imputing missing data:

Missing scores before the first non-missing score will be replaced by the median score at the missing time point from other subjects in the same treatment group. Missing scores after the last non-missing score will be replaced by the last non-missing score (last observation carried forward). Linear interpolation will be used to replace missing scores between two non-missing scores. Subjects who have no pain scores after surgery will have the missing scores replaced by the median score at the missing time point from other subjects in the same treatment group.

Additional methods for dealing with missing data will be described in the SAP.

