7. STATISTICAL METHODS OF ANALYSIS

7.1. General Principles

Descriptive statistics (the number of subjects [n], mean, standard deviation [SD], median, minimum, and maximum) will be used to summarize continuous variables. Means and medians will be presented to one more decimal place than the recorded data. Standard deviations will be presented to two more decimal places than the recorded data. Minimum and maximum values will be presented using the same number of decimal places as the recorded data. Percentages will be presented to one decimal place.

In addition, for PK parameters, geometric means and between-subject coefficient of variations (%CV) will be presented.

Frequency distributions (number [n] and percentage of subjects [%]) will be used to summarize categorical or qualitative variables. In general, the denominator for the percentage calculation will be based upon the total number of subjects in the study population for the treatment groups, unless otherwise specified.

All statistical tests will be performed against a two-sided alternative hypothesis with a significance level of 5% ($\alpha = 0.05$), and all confidence intervals (CIs) calculated will be two-sided 95% CIs. All tests will be declared to be statistically significant if the calculated p-value is ≤ 0.05 unless specified otherwise. Tests for binomial proportions will be conducted (1) using a normal approximation whenever each classification cell for each group to be compared contains expected cell counts of 5 or more subjects, or (2) using an exact method whenever any one classification cell for any one group to be compared contains expected cell counts of fewer than 5 subjects.

All analyses will be performed using SAS[®] Software version 9.2 or later.

Pharmacokinetic parameters will be derived using noncompartmental methods with WinNonlin[®] Professional Version 5.2 or later (Pharsight Corp., Cary, North Carolina).

For the listings, subjects will be listed under their randomized treatment, regardless of actual treatment received. Subjects who are randomized but do not receive study drug will be included in the listings with the treatment group identified as “Liposome bupivacaine xx mg, Not Treated” or “Placebo, Not Treated”, depending on their randomized treatment.

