7.1.2. Imputation of NRS Pain Intensity Scores

For calculation of AUC of NRS pain intensity scores, the windowed worst observation carried forward (wWOCF) and last observation carried forward (LOCF) imputation procedure will be used as follows:

- a) Windowed worst observation carried forward for rescue medications

For subjects who take a rescue medication, their NRS scores recorded within the window of controlled type of rescue medication (see the table below for the windows for the planned rescue medications) will be replaced by the ‘worst’ observation. The worst observation will be the highest score in the time interval from Time 0 to up to the time prior to taking the first rescue medication. The NRS score at the first rescue will be included in this calculation. Note that NRS scores in the window that are higher than the worst value prior to rescue medication will not be overwritten. If no NRS score is available prior to the first rescue the worst observation from all available NRS scores will be used instead.

Medication	Route	Window Used to Impute NRS
Oxycodone	PO	6 hours
Oxycontin (MS Contin)	PO	6 hours
Morphine	IV	4 hours
Hydromorphone (Dilaudid)	IV	2 hours
Hydromorphone (Dilaudid)	PO	4 hours
Fentanyl	IV	6 hours
Fentanyl	Transdermal	Start of administration until the end of the administration plus 6 hours
Hydrocodone	PO	6 hours
Bupivacaine HCl	Perineural	12 hours
Bupivacaine HCl	Infusion	Start of the infusion until the end of the infusion plus 12 hours

Ropivacaine		Start of the infusion until the end of the infusion plus 12 hours
Meperidine	IV	4 hours
Ultram	PO	6 hours

IV = intravenous; PO = oral.

If unplanned rescue medications are given then the window will be determined post-hoc prior to breaking the blind. If a combination opioid is given then the window will be determined by the opioid part of the medication. Opioids given postsurgically with an indication like ‘anesthesia maintenance’ will not be included for imputation purposes.

- b) Missing scores before the first non-missing score will be replaced by the median score at the missing time point from the other subjects in the same treatment group.
- c) Missing scores after the last non-missing score will be replaced by the LOCF.
- d) Missing scores between two non-missing scores will not be replaced (i.e., linear interpolation will be used).

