Subjects who have no pain intensity scores recorded after surgery will have the missing scores replaced by the median score at each time point from all subjects in the same treatment group.

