8. SAMPLE SIZE CALCULATIONS

Part 1

The sample size for Part 1 of the study was not based on formal statistical power calculations.

Part 2

A study population of approximately 180 subjects is planned with approximately 90 subjects in each treatment group (liposome bupivacaine and placebo). The sample size was estimated based on the results of a Phase 3 hemorrhoidectomy study of liposome bupivacaine versus placebo where the mean (SD) AUC of the NRS-R pain intensity scores through 72 hours was 141 (101) and 202 (104) for the liposome bupivacaine and placebo groups, respectively.

A two-group t-test with 0.05 two-sided significance level will have >97% power to detect a difference in means of 61, assuming that the common SD is 104, when the sample size in each group is 90.

After the data from Part 1 are evaluated, the sample size for Part 2 may be increased. The evaluation of the data did not indicate that the sample size should be increased.

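### Empty pain profiles are filled with the subject's own arm's medians and analysed as observed, making the primary test anti-conservative by an amount that depends on an unstated fraction filled

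*SAP*

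**What the plan says.** The rule that matters most is the closing paragraph of SAP 7.1.2. Subjects with no pain score after surgery "will have the missing scores replaced by the median score at each time point from all subjects in the same treatment group". SAP 7.1.2(b) handles a profile that starts late: scores missing before the first recorded one are "replaced by the median score at the missing time point from the other subjects in the same treatment group". Protocol 15.5 has both rules, in each case with the missing scores "replaced by the median score at the missing time point from other subjects in the same treatment group".

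Such subjects are not removed elsewhere. The efficacy set (SAP 6, protocol 15.4) asks only for study drug and the planned surgery, not for a pain score. SAP 7.6.2.1 puts the resulting AUC into an ordinary ANCOVA with treatment and baseline NRS-R, and reports LS means, a 95% CI and a p-value. There is no multiple imputation and no variance correction. The only sensitivity analysis of the primary endpoint drops subjects with interval data from the PCA pump, which is a different problem. Under SAP 7.1.4 the two secondary endpoints are tested only if the primary test is significant.

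**The concern.** The fill value depends on treatment arm. Each filled subject is a near copy of the centre of his or her own arm. That has two effects. Any chance difference between the arms is repeated in the filled values, and the within-arm SD shrinks while the subject still counts fully in N. The model therefore reports a standard error smaller than the real one, even when scores are missing completely at random and equally often in both arms. At stake are the confidence interval and p-value of the single primary test, and with them entry to the secondary tests.

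**Working it through.** **Inputs.** SAP 8 gives the Part 2 design: "A two-group t-test with 0.05 two-sided significance level will have >97% power to detect a difference in means of 61". The SD behind this is 104 for both arms, with 90 subjects per arm (same section) and 1:1 allocation (protocol 9.1). Scores are due at 2, 4, 8, 12, 24, 36, 48, 60 and 72 h (protocol 12.1), with the time-0 score set to 0 (SAP 7.1.1). The documents give no missing-data rate, so the fraction filled, f, is assumed.

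**1. The plan's own figure.** SE of the difference = 104 × √(2/90) = 15.50. 61/15.50 = 3.93, and 3.93 − 1.96 = 1.97, so power is 97.6% (97.5% with the exact t distribution). The stated figure of more than 97% is reproduced.

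**2. Effect of filling, by formula.** Let a fraction f of each arm be filled at the arm's centre, treated here as its mean.

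- True variance of the arm mean: σ²/[(1−f)n], since only (1−f)n subjects carry information.
- Reported variance: (1−f)σ²/n, since the sample variance shrinks by 1−f and N stays at n.
- Reported SE / true SE = 1−f, so type I error ≈ 2[1 − Φ(1.96(1−f))].

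| f | 1% | 2% | 5% | 10% | 20% |
|---|---|---|---|---|---|
| Type I error | 5.2% | 5.5% | 6.3% | 7.8% | 11.7% |

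On the plan's scale at f = 10%, the true SE is 104 × √(2/81) = 16.34 and the reported SE is 0.90 × 16.34 = 14.71.

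**3. Null simulations, 90 per arm, own-arm median fill.** These use several score models. Rescue windows were not modelled in sets B and C. Monte Carlo SE is √(0.05 × 0.95/20,000) ≈ 0.15 points, or 0.24 points for 8,000 runs.

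| Set | 1/90 or 1% | 2/90 or 2% | 4/90 or 5% | 9/90 or 10% |
|---|---|---|---|---|
| A: 8,000 runs, AUC SD about 103 | – | – | 6.0% | 7.8% |
| B: 20,000 runs, ANCOVA, AUC SD about 100 (percentages) | 5.13% | 5.11% | 5.88% | 6.84% |
| C: 20,000 runs, t-test, AUC SD about 115 | 5.4% | 5.8% | 6.5% | 8.6% |
| D: 8,000 runs, two-group test | 5.35% | 4.95% | 6.1% | 7.5% |
| E: 20,000 runs | 5.1% | 5.6% | 5.6% | 6.3% |

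Set B with nothing missing gave 5.13%, and its ratio of reported to true SE was 0.962 at 5% and 0.927 at 10%. The spread between sets probably reflects the integer scale. An arm's median moves in jumps, so it may be identical in both arms or may vary more than the mean does.

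**4. Late starters.** Trapezoid weights are 2 h (at 2 h), 3 h (4 h), 4 h (8 h) and 8 h (12 h) out of 72. The 2 h and 4 h scores carry 5/72 = 7% of the AUC, and the scores from 2 to 12 h carry 17/72 = 24%. In set B, with 20% of subjects affected, type I error was 5.24% if the 2 h score is missing, 5.25% if 2 h and 4 h are, and 5.94% if all of 2 to 12 h are. With 50% missing all of 2 to 12 h it was 8.91%.

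**5. Alternatives.** With a fill common to both arms, the estimate becomes (1−f) times the observed difference. The variance of each arm mean is then (1−f)²σ²/[(1−f)n] = (1−f)σ²/n, apart from the shared fill value, which cancels between arms. This equals the reported variance, so the test is nominal. Simulated type I error with pooled fill was 4.6% and 5.4% (A, at 4/90 and 9/90), 4.9-5.0% (C) and 4.8-5.3% (E). Leaving empty profiles out gave 4.96% and 5.15% at 5% and 10% (B), and power for 61/104 of 97.0% and 96.2%.

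Coverage of the 95% CI at 9/90 with a real effect, in two sets of runs: own-arm fill 92.9% and 92.8%; pooled fill 94.2% and 93.0%; empty profiles left out 95.2% and 94.9%.

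**The case against.** The best defence is rarity. To be wholly filled, a subject must be dosed and operated on and then give no score at any of nine assessments. Subjects stay at the site for at least 72 h, and protocol 13.1 puts data collection through the primary endpoint under staff supervision. A subject with even one score who then withdraws is handled by LOCF, and gaps between scores are interpolated; neither uses the median rule. At 1-2% filled, sets B and D show no inflation beyond simulation error. All of this stands, and it limits the likely size. It does not make the rule valid, and no other provision compensates: the worst-observation rule replaces recorded scores, so an empty profile gives it nothing to act on.

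Three stronger readings are tempting, and the documents do not support them.

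- A reader might infer that this trial's primary test is materially anti-conservative, for example at 7.8%. That needs about 10% of profiles empty and a particular score model, and nothing in the documents points to such a fraction.
- A reader might give the late-start rule equal weight. Step 4 shows otherwise.
- A reader might object that an own-arm fill cannot be computed on blinded data. That is true but breaks no commitment: only windows and conversion factors for unplanned rescue drugs must be settled before unblinding (SAP 7.1.2 and 7.6.2.2).

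It can also be said that the pooled median is still single imputation. That stands too, and is why the fix includes an analysis without empty profiles.

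**Conclusion.** The concern holds in conditional form. Filling an empty profile with own-arm medians and analysing it as observed understates the standard error and makes the primary test anti-conservative, to a degree set by the fraction filled. At 1-2% the excess is negligible to about half a percentage point (0.8 points in the least favourable simulation, set C against its own pooled fill). At 4-5% type I error is about 5.6-6.5%, and at 10% about 6.3-8.6%. Supervised inpatient follow-up makes the low end more likely, but the documents do not bound the fraction. The late-start rule shares the flaw with little effect unless many subjects miss every score through 12 h.

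The figures assume missingness completely at random and equally frequent in both arms. If missingness depends on pain or differs by arm, own-arm filling can also bias the estimate; that was not quantified.

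**What to change.** In SAP 7.1.2(b), the closing paragraph of SAP 7.1.2, and both median sentences of protocol 15.5, replace the median of the subject's own treatment group with the median pooled over all treatment groups within the same study part. This restores the type I error.

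Report the number of filled profiles per arm, separating wholly empty from late-starting ones. Add a sensitivity analysis of the primary endpoint that leaves out subjects with no postsurgical score. It is needed because the pooled fill shrinks the estimated difference by about the fraction filled (at 5%, from 61 to 0.95 × 61 = 58) and does not by itself give an exact confidence interval.

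The cost is a wording change in three places, a small programming change and one extra table, with no new data. The estimate and power become slightly less favourable. The change should be made before Part 2 is unblinded, so that the counts per arm cannot influence it.

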7.1.3. Handling Missing Values

Surgery Date or Time

It is expected that all necessary information on surgery (start and stop date and time) and postsurgery rescue medication (start dates and times, doses, frequency) will be complete. Any such information that is missing and cannot be obtained through query resolution may be imputed, on a case-by-case basis, in a conservative manner that minimizes bias. For example, if pain medication taken on Day 1 has no time of administration recorded, the imputed time will be the end of surgery.

PCA Pump Interval Data

For some subjects, individual doses from the PCA pump were not collected. For some subjects the individual doses were not collected for the whole 72 hours and for some it was not collected for parts of the 72 hours. For these data the intervals during which medication was delivered via the PCA pump are known. So what was entered in the database was the medication, the start date and time of the interval, the stop date and time of the interval, and the total dose received.

For these cases, for purposes of imputing pain scores using the wWOCF imputation, it will be assumed that a dose was given at the beginning of the interval, a dose was given at the end of the interval, and a dose was given in the middle of the interval.

For these cases, for purposes of calculating the total postsurgical opioid consumption through the various time intervals, it will be assumed that the total dose was given at the beginning of the interval.

Rescue Pain Medication

For calculation of the total rescue pain medication usage (morphine equivalent) by time point, if a subject is discontinued early (e.g., dies, withdraws consent, is withdrawn from the study, or is lost to follow-up) before the end of the time interval (e.g., 24 hours after study drug administration), his or her total rescue pain medication usage through the time interval will be a projected amount. For example, if a subject discontinues early at 6 hours after surgery, the projected amounts through 24 hours will be actual amount + average amount (actual amount/6 hours) multiplied by the number of hours remaining in the time interval (24-6).

Adverse Event or Concomitant Medications Dates or Times

For AEs or concomitant medications with missing or partially missing start/stop date/time, the following imputation rules will be applied:

For partial start date/time:

- If the year is unknown, then the date will not be imputed and will be assigned a missing value.
- If the month is unknown, then:
 - i) If the year matches the year of the dose of study drug date, then the month and day of the dose of study drug date will be imputed.
 - ii) Otherwise, 'January' will be assigned.
- If the day is unknown, then:
 - i) If the month and year match the month and year of the dose of study drug date, then the day of the dose of study drug date will be imputed.
 - ii) Otherwise, '01' will be assigned.
- If the time is unknown, then:
 - i) If the date (day, month, and year) match the date of the dose of study drug date, then the time of the dose of study drug time will be imputed.
 - ii) Otherwise, "00" will be assigned.

For partial stop date/time:

- If the year is unknown, then the date will not be imputed and will be assigned a missing value.
- If the month is unknown, then 'December' will be assigned.
- If the day is unknown, then the last day of the month will be assigned.
- If the time is unknown, then the last time of the day will be assigned.

If the above rules for stop dates result in an illogical date with regards to the dates the subject is in the study, then the stop date will be replaced with the subject's date of completion/ withdrawal. Further, should the above rules not result in the most conservative date, then the imputed value may be replaced by a date that will lead to a more conservative analysis. Should this situation arise, specific details will be provided in the derived dataset specification documentation or documented in the derived analysis data set program using comments.

AE Severity or Relationship to Study Drug

If severity of an AE is not reported, then for tables of AEs by severity, the event will be classified as 'Severe'. If relationship to study drug is not reported for an AE, then for tables of study-drug related AEs, the event will be classified as related.

Time to Event Time

For calculating time to an event when only the hour, and not the minutes, are reported for the time of the event, then the minutes will be set to zero.

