7.1.1. Calculation of AUC of NRS

Area under the curve (AUC) will be calculated using the trapezoidal method with the actual NRS pain intensity scores reported by the subject. Missing values will be imputed as described in [Section 7.1.3](#). The time points “Baseline” and “First Rescue” will not be included in the calculation of AUC. However, “First Rescue” might be used for imputation purposes as described in [Section 7.1.2](#). Time 0 NRS score will be set to a score of 0. Actual times, not scheduled times, when available will be used in the calculations. Linear interpolation will be used to calculate the pain intensity score at the end of an interval. For 72 hours, as an example, if the actual time is prior to 72 hours post-dose then the actual time

and the reported score will be used. In addition, the reported score will be carried forward to 72 hours. If the actual time is after 72 hours then linear interpolation between the 60-hour and 72-hour scores will be used to calculate the score at 72 hours and the time will be set to 72. The linear interpolation will be performed after missing pain scores are imputed as discussed in Section 7.1.2.

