7.6.2. Methods of Analysis

7.6.2.1 Primary Efficacy Variable

The primary efficacy variable is the AUC of the NRS-R pain intensity scores through 72 hours using the wWOCF + LOCF imputation method described in [Section 7.1.2](#).

Each dose of liposome bupivacaine (Part 1) and the one dose of liposome bupivacaine (Part 2) will be compared to placebo using analysis of covariance (ANCOVA) with treatment as the main effect and the baseline NRS-R pain intensity score as the covariate. Based on the model, the least squares (LS) means, LS mean difference between the two treatment groups, 95% CI for the LS mean difference(s) between liposome bupivacaine and placebo, and p-value will be reported.

For Part 2, descriptive statistics of the primary efficacy variable will also be shown by site.

Sensitivity Analyses of the Primary Efficacy Variable

For Part 2 a sensitivity analysis will be performed.

The sensitivity analysis will exclude subjects who had interval data for opioid consumption.

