7.6.2.3 Tertiary Efficacy Variables

For Part 1, no statistical tests will be performed on any of the tertiary efficacy variables. Only descriptive statistics will be shown for each treatment.

For Part 2, the following describes the statistical analyses to be performed.

NRS-R, NRS-A, and AUC of Pain Intensity Scores

For the tertiary efficacy variables NRS-R, NRS-A, and the AUCs of the NRS-R and NRS-A pain intensity scores, the same analyses as those for the primary efficacy variable will be performed, except that the baseline NRS-A score will be used as the covariate for all variables using the NRS-A.

Proportion of Subjects Who are Pain Free

Pain free is defined as an NRS-R pain intensity score of 0 or 1. The number and percentage of subjects who are pain free will be summarized by treatment group for each time point. A chi-square test will be used to compare liposome bupivacaine to placebo.

Total Postsurgical Opioid Consumption Through 24, 36, 48, and 60 Hours

For the tertiary efficacy variables total opioid consumption through each of the time periods, the same analysis as that for the secondary efficacy variable of total opioid consumption through 72 hours will be performed.

Subjects Who Receive Rescue Medication

The category of ‘Subjects who receive no rescue medication’ is defined as subjects who report not taking any medication on the four Rescue Medication eCRFs.

The category of ‘Subjects who only receive the IV hydromorphone bolus’ is defined as subjects who report taking IV hydromorphone (or other opioid medications) on the First Rescue Medication eCRF and report not taking a medication on either of the Second Rescue Medication eCRFs or on the Third Rescue Medication eCRF.

The category of ‘Subjects who receive the IV hydromorphone bolus and a second opioid medication’ is defined as subjects who report taking IV hydromorphone (or other opioid medication) on the First Rescue Medication eCRF and who report taking a medication on either of the Second Rescue Medication eCRFs and report not taking a medication on the Third Rescue Medication eCRF.

The category of ‘Subjects who receive the IV hydromorphone bolus, a second opioid medication, and conventional bupivacaine HCl’ is defined as subjects who report taking IV hydromorphone (or other opioid medication) on the First Rescue Medication eCRF, who report taking a medication on either or both of the Second Rescue Medication eCRFs, and bupivacaine HCl on the Third Rescue Medication eCRF.

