wWOCF + LOCF = imputation using the worst observation prior to the use of rescue medication within a medication window and last-observation-carried-forward for missing values.

Reference: [Listings 16.5.1.1](#) and [16.5.1.2](#).

Pacira Pharmaceuticals, Inc.
402-C-323

Table 14.2.2.1.3-2 (Page x of Y)
AUC of NRS-R Pain Intensity Scores Through 72 Hours
wWOCF + LOCF Imputation for the Pain Scores Excluding Subjects with PCA Interval Data
Study Part 2
(Efficacy Analysis Set)

Statistics	LB XXX mg (N=XX)	Placebo (N=XX)
n	00	00
Mean	000.0	000.0
SD	00.00	00.00
Median	0000	0000
Minimum, Maximum	000, 000	000, 000
LSM (Standard Error) [1]	00.0 (00.00)	00.0 (00.00)
LSM Difference (Standard Error) [2]	00.0 (00.00)	
95% CI for Difference [2]	00.0, 00.0	
P-value [2]	0.0000	

AUC = area under the curve calculated using the trapezoidal method; CI = confidence interval; LB = liposome bupivacaine; LSM = least squares mean; NRS-R = numeric rating scale at rest.

Scores are based on a numeric rating scale where 0 = no pain and 10 = worst possible pain.

wWOCF + LOCF = imputation using the worst observation prior to the use of rescue medication within a medication window and last-observation-carried-forward for missing values.

[1] From an analysis of covariance with treatment as the main effect and the baseline NRS-R pain intensity score as the covariate.

[2] Difference from placebo.

Reference: [Listings 16.5.1.1](#) and [16.5.1.2](#).

Pacira Pharmaceuticals, Inc.
402-C-323

Table 14.2.2.2-2 (Page x of Y)
Total Postoperative Consumption (mg) of Opioid Rescue Pain Medication Through 72 Hours
Study Part 2
(Efficacy Analysis Set)

Statistics	LB	Placebo
	67 mg (N=XX)	(N=XX)
n	00	00
Mean	00.00	00.00
SD	00.000	00.000
Median	00.00	00.00
Minimum, Maximum	00.0, 00.0	00.0, 00.0
Geometric LSM [1]	00.00	00.00
Geometric LSM Ratio [2]	00.00	
95% CI for Ratio [2]	00.00, 00.00	
P-value [2]	0.0000	

CI = confidence interval; LB = liposome bupivacaine; LSM = least squares mean.

If the total amount of opioid used was 0 mg, the value was set to the lesser of 1 mg or one half of the smallest total amount observed in the study prior to being transformed into the natural logarithm.

[1] From an analysis of variance with treatment as the main effect on natural log transformed opioid amount.

Results are presented in the original, non-transformed scale.

[2] Geometric LSM Ratio is the anti-log LSM difference (LB/placebo).

Reference: [Listing 16.5.2.1](#).

Pacira Pharmaceuticals, Inc.

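### The three-dose rule for PCA intervals is never varied in the full efficacy set, and start-of-interval dosing overstates the tertiary 24 to 60 h opioid totals

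*SAP*

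**What the plan says.** SAP 7.1.3 (PCA Pump Interval Data) reports that bolus-level PCA records are missing for some subjects, for all or part of the 72 hours. For those stretches the database holds the drug, the interval start, "the stop date and time of the interval, and the total dose received". Two conventions follow.

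- For imputing pain scores: "it will be assumed that a dose was given at the beginning of the interval, a dose was given at the end", and a third dose in the middle.
- For opioid consumption: "it will be assumed that the total dose was given at the beginning of the interval".

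The first convention feeds SAP 7.1.2, where "their NRS scores recorded within the window of controlled type of rescue medication" are replaced by the worst score before first rescue, unless already higher. The window is 4 h for IV morphine and 2 h for IV hydromorphone. SAP 7.1.1 adds: "Actual times, not scheduled times, when available will be used in the calculations".

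SAP 7.6.2.1 plans one sensitivity analysis of the primary variable, in Part 2 only: "The sensitivity analysis will exclude subjects who had interval data for opioid consumption". Its table is titled "wWOCF + LOCF Imputation for the Pain Scores Excluding Subjects with PCA Interval Data". For opioid totals through 24, 36, 48 and 60 h, SAP 7.6.2.3 states that "the same analysis as that for the secondary efficacy variable of total opioid consumption through 72 hours will be performed".

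**The concern.** Interval length and total dose are both recorded, yet neither enters the imputation rule. A 2 h interval and a 24 h interval each receive three nominal doses, as do light and heavy users. In a long interval with frequent boluses, scores taken during PCA use can enter the primary AUC unadjusted. With sparse use, the same rule can replace scores that bolus-level records would have left alone.

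No planned analysis keeps everyone and changes the rule. The exclusion analysis conditions on a feature that arises after randomisation and that only PCA users can have.

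The consumption convention errs in one direction only. It can never understate a cumulative total, and it overstates one whenever part of an interval's dose was used after the cut-off. Those totals are formally tested in Part 2.

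**Working it through.** **1. Scale.** SAP 8 plans on a difference of 61, SD 104, 90 per arm, two-sided 0.05. The standard error is 104 × √(2/90) = 15.5, and 61/15.5 = 3.93. Power is 97.6% (normal approximation) or 97.5% (noncentral t, 178 df), which reproduces the plan's figure of more than 97%.

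**2. Coverage.** With window w and interval length L, the start and middle doses act inside the interval and the end dose acts after it. Hours covered inside = min(L, 2w); total including the tail = min(L, 2w) + w. The caps are 8 h inside and 12 h in total for morphine, and 4 h and 6 h for hydromorphone.

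| L | Morphine, share covered | Hydromorphone, share covered |
|---|---|---|
| 4 h | 100% | 100% |
| 8 h | 100% | 50% |
| 12 h | 67% | 33% |
| 24 h | 33% | 17% |

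**3. One subject by hand.** Assume nominal times, observed score 3 throughout, worst pre-rescue score 7, and Time 0 score 0 (SAP 7.1.1).
- No replacement: 3 + 70 × 3 = 213. All scores replaced: 7 + 70 × 7 = 497.
- One morphine interval, 1-72 h: nominal doses at 1, 36.5 and 72 h cover the 2, 4 and 72 h scores. AUC = 7 + 14 + 20 + 156 + 60 = 257, against 497 if the whole interval counts as covered.
- One interval, 13-35 h, whose only true bolus was at its start: the rule also covers the 24 and 36 h scores, adding 2 × 4 × 12 = 96, so 309 instead of 213.

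The error can go either way.

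**4. Averaged over timing.** Simulation, 20,000 draws. Assumptions: raw score 4, worst 7; assessments jittered within the Protocol Table 1 windows; PCA start uniform on 0.75-6 h; first IV hydromorphone bolus half an hour earlier with its own window; back-to-back intervals to 72 h; no oxycodone. Entries are mean subject AUC under the three-dose rule minus the comparator, for interval lengths 4/8/12/24 h.

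| Comparator | Hydromorphone | Morphine |
|---|---|---|
| Whole interval plus window (upper bound) | 0/-104/-130/-186 | 0/0/-55/-180 |
| Recorded boluses every 4 h | +109/+5/-21/-77 | +4/+4/-51/-176 |
| Recorded boluses every 12 h | about +26/+53/+64/+7 | about +79/+137/+135/+10 |

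In the last row, intervals containing no bolus are left out, because SAP 7.1.3 describes intervals in which drug was delivered. If PCA stops at 24 h and oxycodone every 6 h follows, the first row shrinks to 0/-31/-44/-56 and 0/0/-19/-49. The last row, for 12/24 h intervals, shrinks to +11/0 and +31/0.

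**5. Arm level, illustrative.** Assume 20% interval subjects in each arm with identical intervals, and boluses every 2 h on placebo and every 6 h on active drug. Recorded boluses would separate these subjects by 485 - 354 = 131 (hydromorphone) or by 60 (morphine). The rule separates them by 0. The overall difference shrinks by 0.2 × 131 = 26 or 0.2 × 60 = 12, against 61 planned, or by 7.5 or 3 if PCA ends at 24 h. With equal use the shift is 0.

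**6. Opioid totals.** Assume even use and intervals back to back from hour 1, the last 24 h interval cut at 72 h. The ratio at cut-off H is hours of use credited / (H - 1).

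| Intervals | 24 h | 36 h | 48 h | 60 h |
|---|---|---|---|---|
| 8 h | 24/23 = 1.04 | 40/35 = 1.14 | 48/47 = 1.02 | 64/59 = 1.08 |
| 12 h | 24/23 = 1.04 | 36/35 = 1.03 | 48/47 = 1.02 | 60/59 = 1.02 |
| 24 h | 24/23 = 1.04 | 48/35 = 1.37 | 48/47 = 1.02 | 71/59 = 1.20 |

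A single 0-72 h interval gives 72/24 = 3.0, 72/36 = 2.0, 72/48 = 1.5 and 72/60 = 1.2. At 72 h the ratio is 1.0 for any interval ending by then. On the log scale, a 20-point arm difference in the share of interval subjects would multiply the geometric mean ratio by exp(0.2 × ln 1.37) = 1.065, or by exp(0.2 × ln 3.0) = 1.25. With equal shares and use it is unchanged.

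**The case against.** The rule is prespecified and identical in both arms, and no bias in the treatment difference has been shown. The documents give no interval counts, lengths or split by arm. In the one arm-level example above, the rule shrinks the difference, which is conservative for efficacy. The windows of the first IV bolus and of any oxycodone also narrow the gap. All of this stands.

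A reader might infer that the exclusion analysis is blind to the problem. It is not. In step 5 the full-set difference falls by 26 or 12. Dropping interval subjects, if they otherwise resemble the rest, restores it, so the two tables would show the gap. The limits of that check are its selection and that it leaves the rule untested in the subjects it affects.

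The case against a rerun is also partly right. Simple alternative rules ignore total dose just as the three-dose rule does, so they cannot reveal an arm difference in PCA intensity within equal intervals. Lower use may instead show up as fewer or shorter intervals.

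Nor should dependence on timing be blamed on 7.1.3 alone. With fully recorded hydromorphone boluses every 4 h and nominal assessment times, PCA starts of 1.5 and 2.5 h give AUCs of 290 and 491.

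On consumption, only tertiary totals are affected, and the common back-to-back cases are mostly small.

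**Conclusion.** The point holds as a minor one. The three-dose rule is insensitive to interval length and total dose, can under- or over-impute, and is not varied in the full efficacy set. Per subject, the simulated gaps run from about -186 to +137 AUC units, under assumed scores, timing and bolus patterns.

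A reader might infer that the primary comparison is biased. The documents do not support that: the size and direction of any effect on the treatment difference are unknown, and it is zero with equal shares, intervals and use. A reader might also infer that the secondary opioid endpoint is wrong, but the 72 h total is unchanged for intervals ending by 72 h. What is established is the upward error in the 24, 36, 48 and 60 h totals whenever use is spread across a cut-off. Its size depends on interval layout and on the even-use assumption.

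**What to change.** **SAP 7.1.3, consumption.** Prorate each interval's total dose uniformly over the interval and count only the part before each cut-off. The same section already uses an average hourly rate to project totals for early discontinuations. The downside is that proration understates early totals if use is concentrated early in the interval.

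**SAP 7.6.2.1.** Keep the three-dose rule as primary and keep the exclusion analysis. Add one Part 2 rerun of the primary ANCOVA in the full efficacy analysis set under two bounding rules:
- one window from interval start to interval end plus the drug's window, the form SAP 7.1.2 already uses for local anaesthetic infusions and transdermal fentanyl;
- one dose at interval start only.

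Report by arm the number of interval subjects, interval lengths, drug and total dose. State that these bounds test sensitivity to coverage only, not to an arm difference in PCA intensity. State also that the whole-interval rule over-imputes when on-demand use is sparse.

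The cost is one extra table, a short descriptive summary and minor programming. Listing 16.5.2.2 already carries the drug, start, stop and total dose.
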